İZMİR KÂTİP ÇELEBİ UNIVERSITY
INTERVENTIONAL CLINICAL STUDIES INSTITUTIONAL REVIEW BOARD

To: Asst. [name] [name], PhD

From: Assoc. [name] [name], MD, Chair

Date: 22.05.2025

IRB#:59

Study Title: A Comparative Clinical Evaluation of Two Resin-Based Fissure Sealants Applied with Different Isolation Techniques: An 18-Month Follow –Up Study

At its board meeting on 22.05.2025 your submission for the above referenced research study has received review and approval from İzmir Katip Çelebi Interventional Clinical Studies Institutional Review Board.

A handwritten signature in blue ink, appearing to read '[name]', is placed here.

Assoc. [name] [name]
Chair

Study Protocol with Statistical Analysis Plan, Informed Consent Forms, Ethical Approval

Materials and Method

Study Design

The randomized, controlled, single-blind study was approved by the Medical Ethics Committee of Izmir Katip Celebi University (approval number: 2025/059). Prior to the initiation of treatment, written informed consent was obtained from the parents of the children participating in the study. The study was conducted in accordance with the CONSORT (Consolidated Standards of Reporting Trials) guidelines to ensure transparent and comprehensive reporting of the clinical trial methodology and findings.

Sample Size

The estimation of sample size was conducted utilizing G*Power 3.1.9.7 software (Germany). According to the statistical parameters reported in a reference study,²² the effect size was set at 0.56, the alpha error at 0.05, and the power of the study at 0.81. It was determined that, in consideration of the established parameters, the minimum requisite sample size was to be calculated as 43 teeth per group. However, to account for an estimated loss of 20 of participants, which is a common occurrence in pediatric clinical studies due to factors such as non-compliance, anxiety, or missed follow-up appointments, the target sample size was adjusted to 50 teeth per group. Consequently, a total of 200 teeth (100 teeth per material and 50 teeth for four subgroups) was established to ensure sufficient statistical power and maintain the validity of the study despite potential participant loss.

Sample Inclusion and Exclusion Criteria

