The study comprised 100 healthy children aged between 6 and 12 years, with a mean age of 7.9 years, ASA class I (American Society of Anesthesiologists), who were determined to exhibit cooperative behavior with a score of 3 or 4 on the Frankl Behavior Rating Scale. All participants had fully erupted lower first permanent molars on both sides (200 teeth), which

required the application of pit and fissure sealants. The inclusion criteria were based on the International Caries Detection and Assessment System II (ICDAS II) criteria, including deep and retained pits and fissures, no restorations, and no evidence of caries lesions. Participants with special needs or systemic disease (ASA classification II or higher), requiring emergency dental care, suffering from a severe gag reflex or an allergy to latex, exhibiting uncooperative behavior (Frankl Score 1 or 2), exhibiting molars with anomalies of the enamel/dentin, or unable to attend follow-up appointments were excluded from the study.

Screening Participants

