A split-mouth study design was employed, whereby two different fissure sealant materials were applied using two different isolation techniques. Each patient received both sealants, with one applied under rubber dam isolation and the other under cotton roll isolation. The allocation of materials and isolation methods to specific teeth was randomized to minimize bias. A computer-generated randomized list *Research Randomizer (Ver;4.0)* was employed to determine the sequence of application of fissure sealant materials, as well as the side (right or left mandibular molar) on which each material would be applied. In accordance with the sealant material and isolation protocol, this randomized process resulted in the formation of four different study groups.

- (a) a highly filled fluoride-containing fissure sealant with rubber dam isolation,
- (b) a highly filled fluoride-containing fissure sealant with cotton roll isolation,
- (c) an unfilled fluoride-containing fissure sealant with rubber dam isolation,
- (d) an unfilled fluoride-containing fissure sealant with cotton roll isolation.

The chemical composition, manufacturer, and application procedures of the tested fissure sealant materials are shown in Table 1.

Clinical Procedure

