The plaque and debris were removed from the occlusal surfaces using a rotating brush and non-fluoride prophylactic paste. In accordance with the results of the randomization process and following the determination of the materials and isolation methods to be employed on each side of the patient, each tooth was isolated using a rubber dam, an arch and metal clasps, or cotton rolls with a high-volume suction, to avoid contamination from saliva. The application was carried out under proper illumination in accordance with the manufacturers' recommendations, as outlined in Table 1. Following the successful application of the designated sealant to the first tooth, the contralateral homologous tooth was sealed using an alternative material. The polymerisation of all materials was conducted using an LED light-curing unit (Valo, Ultradent Products Inc., South Jordan, Utah, USA), in accordance with the manufacturer's instructions. After each application, the sealant was subjected to testing for the absence of air bubbles, marginal adaptation, retention, and complete polymerisation. If a deficiency was identified, the tooth was re-treated. The occlusion was then subjected to evaluation, with any potential premature contacts being eliminated. All children were provided with oral hygiene instructions and any other necessary dental treatment.

Follow-up

The evaluation of pit-and-fissure sealants was conducted to record the presence of caries lesions and sealant retention at 6-, 12-, and 18-month follow-up visits. The evaluation was performed by one calibrated pediatric dentist, who was unaware of which sealant had been used and the teeth were air-dried and observed under appropriate illumination following toothbrush prophylaxis. The International Caries Detection and Assessment System (ICDAS) II criteria were employed to record caries lesions and following classification system was employed for the retention evaluation of the sealants: 1 = complete retention; 2 = partial loss; or 3 = complete loss. The pit-and-fissure sealants that were noted to have undergone complete loss during the

follow-up appointments were subjected to re-treatment, exclusion from the study, and documentation as complete loss until the conclusion of the follow-up period.

Statistical Analysis

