The analysis of the retention rates of the fissure sealant materials was conducted utilizing the IBM SPSS Statistics 30.0 statistical software package (SPSS, Chicago, Illinois, USA). Chi-square tests were used to determine whether there were statistically significant differences in retention rates between sealant materials and isolation techniques at different time points at the five percent significance level. The Kaplan-Meier survival analysis was applied to assess the cumulative retention rates of the sealants over time. The Log-Rank test was utilized to compare the survival distributions between different groups. The median and mean survival times for each fissure sealant and isolation technique were calculated, along with their 95% confidence intervals (CI).

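### The split-mouth pairing is ignored: chi-square and log-rank tests for independent teeth are conservative, and weaker than a paired analysis, when the two teeth of a child are positively correlated

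*Combined protocol and SAP*

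**What the plan says.** The design is paired. Under Blinding and randomization: "Each patient received both sealants, with one applied under rubber dam isolation and the other under cotton roll isolation". Under Clinical Procedure, once the first tooth was sealed, "the contralateral homologous tooth was sealed using an alternative material". Under Sample Inclusion and Exclusion Criteria, 100 children supply two teeth each: "All participants had fully erupted lower first permanent molars on both sides (200 teeth". Sample Size then counts "a total of 200 teeth (100 teeth per material and 50 teeth for four subgroups".

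The Statistical Analysis section is a single paragraph. For retention: "Chi-square tests were used to determine whether there were statistically significant differences in retention rates between sealant materials and isolation techniques", at each time point and at the 5% level. For survival, after Kaplan-Meier estimation: "The Log-Rank test was utilized to compare the survival distributions between different groups". It names no McNemar test, conditional or mixed model, GEE, stratified log-rank, frailty or robust variance, and no other section supplies one.

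**The concern.** Label the four groups as the protocol does: (a) filled sealant with rubber dam, (b) filled with cotton roll, (c) unfilled with rubber dam, (d) unfilled with cotton roll. Both factors must differ between a child's two teeth, so every child is either an a+d pair or a b+c pair. The 100 teeth per material are therefore 100 matched pairs, and so are the 100 teeth per isolation technique. An ordinary chi-square or log-rank test treats them as 200 unrelated units.

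For a within-child contrast, ignoring a positive correlation makes the standard error too large. The risk is therefore not a false positive. It is a conclusion of no difference between rubber dam and cotton roll, or between the sealants, that arises because the analysis set aside the matching the design provides. Confidence intervals for the differences built on the same variance would be too wide.

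**Working it through.** **Inputs from the documents.** 100 children with two teeth each; 50 teeth in each of a, b, c and d, hence 50 a+d and 50 b+c children; visits at 6, 12 and 18 months; effect size 0.56, alpha 0.05, power 0.81, 43 teeth per group; an expected loss of 20, read as 20%, which leaves 80 children.

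**Assumed, because the documents give no values.** Within-child correlation (a range including 0) and the retention rates.

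**1. The plan's own figure.** With independent groups and a one-sided test, n = 2(1.645 + 0.878)²/0.56² = 40.6, so 41. The t-test gives 42. A Mann-Whitney version at 80% power gives 42.02, so 43, with power 0.808 at 43. Two-sided independent-group formulas give 52 to 55. Paired formulas give 22 (one-sided) or 28 (two-sided). The 43 is thus reproduced by treating teeth as independent, not as pairs.

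**2. Size of the unpaired test, closed form.** With n pairs and common retention p, the true variance of the difference is 2p(1−p)(1−rho)/n. The unpaired test uses 2p(1−p)/n, which is too large by 1/(1−rho). Its true size is 2[1 − Φ(1.96/√(1−rho))]. For rho = 0.32, 1.96/√0.68 = 2.377, giving 1.7%. Interval widths are inflated by 1/√(1−rho): 1.10 at rho 0.18 and 1.39 at rho 0.48.

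**3. Size by simulation** (no true effect, 70% retention, 100 children, correlated binary outcomes, 20,000 replicates; log-rank for two groups on the three visits):

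| Correlation | 0 | 0.18 | 0.32 | 0.48 |
|---|---|---|---|---|
| Closed form | 5.0% | 3.0% | 1.7% | 0.7% |
| Chi-square | 5.1% | 3.1% | 1.8% | 0.7% |
| Ordinary log-rank | 5.0% | 3.0% | 1.7% | 0.6% |

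McNemar stays at 4.9% to 5.4% throughout.

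**4. Power by simulation** (80% versus 65% retention, 80 children):

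| Correlation | 0 | 0.17 | 0.30 | 0.45 |
|---|---|---|---|---|
| Chi-square | 0.57 | 0.58 | 0.60 | 0.60 |
| McNemar | 0.57 | 0.66 | 0.74 | 0.83 |
| Ordinary log-rank | 0.58 | 0.58 | 0.59 | 0.59 |
| Cluster-robust log-rank | 0.57 | 0.65 | 0.73 | 0.83 |

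With 80% versus 62% and all 100 children, at similar correlations, chi-square gives 0.81 / 0.84 / 0.86 / 0.88 and McNemar 0.81 / 0.88 / 0.93 / 0.97. The chi-square test's own power does not fall as correlation rises; the loss is relative to a test that uses the pairing.

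**5. Which comparisons are affected.** a–b, a–c, b–d and c–d compare different children, and ordinary chi-square is correct there (a–b size 4.7% to 4.9%). a–d and b–c are paired (a–d size 2.9% down to 0.7%). A four-group chi-square is mildly conservative (3.7% to 4.0%). The material-by-isolation contrast, (a+d) − (b+c), lies between children. If it were tested with teeth as independent, its size would be 2[1 − Φ(1.96/√(1+rho))], that is 7.1%, 8.8% and 10.7% at rho 0.18, 0.32 and 0.48. The plan names no such test.

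**The case against.** The strongest reply is that the error is on the safe side and may be small. No test the plan names rejects too often while the pair types are balanced, and the correlation is unknown and could be zero. If the plan's 0.56 is read as Cohen's h, it corresponds to about 80% versus 54% retention. With 80 children, chi-square then has power of about 0.94 to 0.98 and McNemar 0.94 to 1.00, a gap of at most about two points. The 80% versus 65% scenario is a smaller effect (h = 0.34).

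That arithmetic is right, but Sample Size does not say what kind of effect size 0.56 is, so the reassurance rests on an assumed reading. It also shows only that a large effect would be found either way. Smaller true differences are where a non-significant result would mislead.

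Two further points stand as limits. The groups in the log-rank sentence could be the four subgroups, in which case an overall test would be less affected than the two-group figures show. The retention score has three levels ("1 = complete retention; 2 = partial loss; or 3 = complete loss") and the plan does not say it is dichotomised, so the binary figures do not carry over exactly to a three-level chi-square. Neither point supplies the missing pairing for the material and isolation comparisons, which the plan names explicitly.

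**Conclusion.** The concern holds. Material and isolation are both within-child factors, and the planned tests use the wrong variance for both whenever the within-child correlation is not zero. With positive correlation the variance is too large by 1/(1 − rho). Over the assumed range of 0.18 to 0.48, true size falls to between about 3% and under 1%. The power forgone against a paired test ranges from nothing at zero correlation to about 23 points (0.83 − 0.60) at 0.45 with 80% versus 65% retention and 80 children. It is smaller for larger effects. These sizes depend on correlations and retention rates that the documents do not give; the mismatch between test and design does not. While a+d and b+c children are balanced, a significant main effect can be believed. A non-significant one should not be read as no difference on these tests.

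**What to change.** 1. Fix the retention outcome in advance, for example score 1 against scores 2 and 3, and use it for both the proportions and the survival analysis; or use an ordinal model.
2. Replace the chi-square tests of material and isolation by a logistic GEE clustered on child, with robust variance and both factors in the model. If the interaction is included, use effect coding or report each main effect averaged over the other factor. A reference-coded material term is a between-child contrast. In a check with 80 children and 80% versus 65% retention, the effect-coded term had power 0.57 to 0.82 as correlation rose from 0 to 0.45 (size 5.2% to 5.6%), while the reference-coded term stayed at 0.29 to 0.31.
3. Use McNemar as a simple alternative only while the pair types are balanced, because material and isolation change together within a child. With no material effect and 80% versus 65% retention by isolation, a McNemar test of material had size 4.5% at 40/40 children, but 7.6% at correlation 0 and 9.1% at 0.30 with a 50/30 split. The two-factor GEE had 5.1% to 5.7% at 50/30.
4. Replace the log-rank test by a Cox or discrete-time model with both factors and child-clustered robust variance, or by a cluster-robust log-rank test. State which groups are compared.
5. Keep ordinary chi-square for a–b, a–c, b–d and c–d, and treat a–d and b–c as paired.

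The cost is revised SAP wording and a different procedure on the same data. No further children or visits are needed, and if the tests have already been run, a re-analysis is enough.

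### The 5% level is attached to each unpaired test of material and isolation at each visit: no primary visit, contrast, order or error rule governs the set, and pairing within the child is ignored

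*Combined protocol and SAP*

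**What the plan says.** The Statistical Analysis section is one paragraph. It compares retention by chi-square between materials and "isolation techniques at different time points at the five percent significance level", then adds Kaplan-Meier curves and log-rank tests between groups that it neither lists nor counts. The Follow-up section records "caries lesions and sealant retention at 6-, 12-, and 18-month follow-up visits" and codes retention as "1 = complete retention; 2 = partial loss; or 3 = complete loss". A sealant completely lost is re-treated, leaves the study and is kept by "documentation as complete loss until the conclusion of the follow-up period".

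The Blinding and randomization section sets up a split-mouth design: "Each patient received both sealants, with one applied under rubber dam isolation and the other under cotton roll isolation". There are thus two arrangements: highly filled under rubber dam with unfilled under cotton roll, or the reverse.

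The Sample Size section states that "the effect size was set at 0.56, the alpha error at 0.05, and the power of the study at 0.81" and plans "a total of 200 teeth (100 teeth per material and 50 teeth for four subgroups". It ties that alpha to no visit, factor or contrast. No section names a primary visit, a primary contrast, an order of testing or a multiplicity rule, or says whether partial loss is a failure for the Kaplan-Meier analysis.

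**The concern.** Two things separate the stated 5% from the error rate of the trial's conclusions.

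First, two factors at three visits give at least six chi-square tests, any of which could be presented as the result. A material difference at 6 months that is absent at 18, or an isolation difference at one visit only, could each support a positive conclusion. The undefined failure event adds another free choice.

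Second, an ordinary chi-square test treats the two compared sets of teeth as independent samples, but here they come from the same children. If a child's two teeth tend to fail or survive together, the test overstates the variance of the difference, rejects too rarely under the null and loses power.

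The two faults push in opposite directions. Their net effect depends on quantities the documents do not give, so the plan cannot be said to run at 5% either per test or overall.

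**Working it through.** **The plan's own figure.** The alpha of 0.05 yields 43 teeth per group. For two means with effect size 0.56 and power 0.81:

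- One-sided: n = 2 × (1.645 + 0.878)² / 0.56² = 40.6, so 41. The t test gives 42, and a Wilcoxon test (efficiency 0.955) gives 43.2, so 44.
- Two-sided: n = 2 × (1.960 + 0.878)² / 0.56² = 51.4, so 52. The t test gives 53.

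The stated 43 is close only to the one-sided answers. The test family and sidedness are not stated, which is a separate matter. What counts here is that the calculation spends the 5% on a single comparison.

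**Independence benchmarks.** 1 − 0.95^k gives 9.75% for 2 tests, 26.5% for 6 (two factors × three visits) and 60.3% for 18 (six subgroup pairs × three visits). These are not the trial's error rates: losses are cumulative, so visits are correlated, and the teeth are paired.

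**Size of one unpaired test.** Let φ be the within-child correlation of the 0/1 failure outcomes. Under the null, with n children, the true variance of the difference in proportions is 2p(1 − p)(1 − φ)/n, while the test uses 2p(1 − p)/n. The true size is therefore about 2Φ(−1.96/√(1 − φ)). At an assumed φ of 0.2 this is 2Φ(−2.19) = 2.8%; at 0.4 it is 2Φ(−2.53) = 1.1%.

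**Simulation under the null.** Inputs from the documents: 100 children with two teeth each, two equal arrangements, three visits, 5% per test. Assumptions: latent-normal loss times; retention at 6/12/18 months of 90/80/70%, 95/90/85% or 80/65/50%; latent within-child correlation from 0 to 0.7. Runs with 80 children are included in the table. Latent correlation is on a different scale from φ. Entries are the probability of at least one p < 0.05.

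| Tests | 0 | 0.3 | 0.5 | 0.7 |
|---|---|---|---|---|
| Six unpaired (two factors × three visits) | 0.191-0.226 | 0.144-0.159 | 0.090-0.115 | 0.038-0.063 |
| One factor, three visits | 0.099-0.121 | 0.074-0.086 | 0.045-0.060 | 0.019-0.033 |
| One unpaired test at 18 months | 0.047-0.058 | 0.028-0.034 | 0.016-0.022 | 0.005-0.010 |
| One four-group test per visit | 0.098-0.121 | 0.084-0.100 | 0.079-0.088 | 0.073-0.085 |

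- Retention matters as well as correlation. At zero correlation, six tests give about 15% with retention 70/67/64%, about 16% with 99/97/95%, and about 23% with 95/85/60%. At correlation 0.3 the wider set of patterns spans about 10-18%.
- If the four subgroups are compared pairwise at each visit (18 tests), the error is about 39-42% at correlation 0 and still about 29-31% at 0.7 under the three main patterns. It is lower at very high retention.
- Log-rank tests: no cap can be given. Two two-group tests add at most 0.4 points if they use the same failure cut as the chi-square. With different cuts they added up to about 2.4 points (0.210 to 0.234, for example).
- Pairing alone does not solve it. Arrangement-stratified paired tests have size 0.040-0.054 each, but all six together give 0.195-0.243.

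**Power.** Material at 18 months, assumed 80% v 65% retention, 100 children, unpaired v paired: 0.66 v 0.66 at correlation 0, 0.68 v 0.75 at 0.3, 0.70 v 0.82 at 0.5, and about 0.72 v 0.90 at 0.7.

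**The case against.** The strongest reply is that at high within-child correlation there is no inflation: at 0.7, six tests together run at about 4-6%. That is correct for the six-test reading. It is not a defence of the plan, because the protection comes from single tests running at about 1% and is paid for in power. It also fails for the other readings: four-group tests stay at 7-9% at 0.7, and pairwise subgroup tests at about 29-31%. The Sample Size section plans by subgroup, so the subgroup reading cannot be dismissed.

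A second reply is that every figure rests on assumed retention and correlation. That stands. The ranges are illustrative, and only the omission itself is certain.

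A third is that the documents already imply the answer. The title reads "A Comparative Clinical Evaluation of Two Resin-Based Fissure Sealants Applied with Different Isolation Techniques: An 18-Month Follow" and continues to the end of its line, so a reader might infer that month 18 is primary and that material ranks before isolation. The title gives a duration and names both factors. The sentence with 100 teeth per material also gives 50 per subgroup, and the calculation itself is per group of 43 raised to 50. The documents declare neither a primary visit nor an order.

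Finally, multiplicity, pairing and the failure definition are separable defects. They are taken together here because correcting one alone leaves a plan that still does not run at 5%.

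**Conclusion.** The point holds as stated. The plan sets a nominal 5% for each test, gives no rule for the set, and uses tests that ignore the split-mouth pairing. For six unpaired tests the chance of at least one false positive is roughly 15-23% with independent teeth and about 4-6% at latent correlation 0.7, with a loss of power in the correlated case. These figures rest on assumed retention rates and within-child correlation, neither of which the documents give.

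A reader might go further and infer that the trial's error rate is 26.5%, or that it is inflated whatever the correlation. Neither is supported. The first needs six independent tests, which these are not. The second is contradicted by the six-test result at 0.7.

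This should be corrected. Confidence is high that the rule is absent and moderate about the size of the consequence.

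**What to change.** 1. Name retention at one visit as primary. Eighteen months is a reasonable choice, being the end of follow-up and the point to which complete losses are carried, but it has to be declared.
2. State whether code 2 (partial loss) is a failure, and report the other cut as a sensitivity analysis.
3. For the primary comparison, replace the unpaired chi-square with a within-child analysis that accounts for the arrangement. One example: take each child's failure difference (highly filled minus unfilled tooth) and average it within each arrangement. Material is the mean of the two averages and isolation is half their difference, each tested with an unequal-variance t test. A GEE or logistic model clustered on child with both factors would also serve.
4. Control the material and isolation tests by Holm at an overall 5%, or by a fixed order that the sponsor chooses and states. With the example analysis at 18 months, simulated false-positive rates were 0.040-0.051 (Holm) and 0.038-0.054 (fixed order), including with unequal arrangements.
5. Report the 6- and 12-month, log-rank and four-group results as secondary, with estimates and confidence intervals and no confirmatory claim.
6. The text is in the past tense. If outcomes have been examined, label the choice of visit, cut and order as post hoc: it then does not restore prespecified error control. The paired analysis is an improvement either way.

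The cost is small: SAP wording and one simple analysis, with no new data. An early-visit result alone can no longer carry the conclusion. There is some loss of power, shown here at 80% v 65% retention and 100 children, for correlation 0 and 0.7:

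- Under Holm with a material effect only, material power falls from 0.66 to 0.55, or from 0.90 to 0.84.
- Under a fixed order with both effects present, computed with isolation second, isolation power falls from 0.68 to 0.45, or from 0.89 to 0.79. If the first factor has no effect, the second is declared only about 3-4% of the time.

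### Kaplan-Meier mean and median times ignore that loss is seen only at months 6, 12 and 18; with visit dating the mean is the highest value the data allow and its 95% CI under-covers

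*Combined protocol and SAP*

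**What the plan says.** The Follow-up section has one blinded examiner record "sealant retention at 6-, 12-, and 18-month follow-up visits", graded "1 = complete retention; 2 = partial loss; or 3 = complete loss". A sealant found completely lost is re-treated, leaves the study, and is carried as "documentation as complete loss until the conclusion of the follow-up period".

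The Statistical Analysis section plans chi-square tests at each time point, Kaplan-Meier curves and log-rank tests. It closes with: "The median and mean survival times for each fissure sealant and isolation technique were calculated, along with their 95% confidence intervals (CI".

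No section says how a loss is dated, mentions interval censoring, gives a restriction time for the mean, or says whether the survival event is any loss or only complete loss.

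**The concern.** A sealant found lost at month 12 was lost at some unknown time after month 6. The loss times are therefore interval-censored, whereas ordinary Kaplan-Meier treats the recorded time as exact. If that time is the visit, the curve stays flat until the visit and then drops, so the area under it is too large. Losses first found at month 18 count as a full 18 months and lower the mean not at all. The confidence interval reflects sampling error only. The median can take no value other than 6, 12 or 18 months, or is not reached.

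The mean and median times are the only quantities for which the plan specifies a confidence interval, so a reader is likely to judge sealants and isolation methods by them. The overstatement grows with the fraction lost, so the worse group is flattered more. The fraction lost in turn depends on the event definition, which the plan leaves open.

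**Working it through.** **Inputs.** Visits at 6, 12 and 18 months (Follow-up). Group sizes: "100 teeth per material and 50 teeth for four subgroups" (Sample Size). "Each patient received both sealants, with one applied under rubber dam isolation and the other under cotton roll isolation" (Blinding and randomization), so a child gives one tooth to each material and one to each isolation method, and a single-group interval has no clustering within child. The 20 given for loss to follow-up is read as 20%, so n = 80 stands for 100 teeth after that loss. The documents state no expected retention and no survival time, so the plan has no figure to reproduce here and all retention levels below are assumptions.

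**1. Limits that need no assumption about shape.** Let S6, S12 and S18 be the proportions retained. Retention cannot rise between visits, so the true mean restricted to 18 months lies between
- lowest: 6 × (S6 + S12 + S18)
- highest: 6 × (1 + S6 + S12)

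The width is 6 × (1 − S18). With visits on schedule, visit-dated Kaplan-Meier returns the highest value. If losses are spread evenly within intervals, the excess is half the width, 3 × (1 − S18).

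**2. Size under a constant hazard.** S(t) = S18^(t/18); the true restricted mean is 18 × (1 − S18) / (−ln S18).

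| 18-month retention | True mean | Visit-dated mean | Excess (months) |
|---|---|---|---|
| 95% | 17.55 | 17.70 | 0.15 |
| 90% | 17.08 | 17.39 | 0.30 |
| 80% | 16.13 | 16.74 | 0.61 |
| 70% | 15.14 | 16.06 | 0.92 |

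(Excesses are from unrounded means.) For 70%: S6 = 0.888 and S12 = 0.788, so 6 × 2.676 = 16.06; the lowest value is 16.06 − 6 × 0.30 = 14.26.

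**3. Coverage by hand.** Take S6/S12/S18 = 0.90/0.80/0.70. Visit-dated times are 6 (probability 0.10), 12 (0.10) and 18 (0.80), with mean 16.2. The variance is 0.10 × 10.2² + 0.10 × 4.2² + 0.80 × 1.8² = 14.76. With even loss the excess is 3 × 0.30 = 0.90 month.
- n = 50: SE = √(14.76/50) = 0.54; excess/SE = 1.66; coverage about Φ(1.96 − 1.66) = 62%.
- n = 100: SE = 0.38; excess/SE = 2.34; coverage about Φ(1.96 − 2.34) = 35%.

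**4. Coverage by simulation** (constant hazard, Greenwood SE, full follow-up, 40,000 replicates), visit-dated, nominal 95%:

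| n | 80% retention | 70% retention |
|---|---|---|
| 100 | 52% | 37% |
| 80 | 58% | 45% |
| 50 | 68% | 61% |

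Exact or midpoint dates at the same settings give about 92–94%. With 16% dropout and n = 50, visit-dated coverage was 67% and 59%. With every loss in the last month of its interval it was still only 86–90%.

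**5. A difference between two means.** For 85% against 70%: true means 16.61 and 15.14 (difference 1.47); visit-dated 17.07 and 16.06 (difference 1.01), so (1.47 − 1.01)/1.47 = 31% too small. Over seven retention pairs between 50% and 95%, the shortfall is 30–33% under constant hazard and 29–43% over Weibull shapes 0.4 to 2.

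With even loss within intervals, the shortfall is 3·D18 / (3·D18 + 6·D6 + 6·D12), where D is the retention gap at each visit:
- whole gap present by month 6: 3/15 = 20%
- gap grows steadily: 3/(3 + 2 + 4) = 33%
- gap nil at month 6 and half at month 12: 3/(3 + 0 + 3) = 50%

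Coverage for the 85% against 70% difference at n = 100 is about 84–89% with unpaired intervals and 76–83% with paired ones (latent within-child correlation 0 to 0.6). In the same simulations a paired interval for the 18-month retention difference covered about 95%.

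**6. Dependence on the dating rule.** With midpoint dating the error in a difference is 0–2% under constant hazard and −5% to +9% over the same shapes.

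**The case against.** The strongest reply is that the plan never says losses are dated at the visit. Midpoint dating would remove nearly all of the error, so the certain defect is a missing rule and not a bias. This stands as a condition on the size. But visits are the only times on record, and nothing in the plan points to another rule.

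Second, no planned test is touched. The chi-square tests, the log-rank test and Kaplan-Meier retention at the visits are not distorted by dating, and the plan names no difference in means. This is correct and limits the point to descriptive summaries.

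Third, read as time to detected loss, the same visit-dated interval covers about 92–94% at 70–80% retention, so the label is at fault more than the arithmetic. That is fair, but the plan presents these figures as survival times without that label.

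Fourth, part of the under-coverage at high retention comes from few events: at 95% retention and n = 50, exact dates cover only 80%, against 66% with visit dates. That holds at 95% but does not explain the figures at 80% and 70%, where exact dates cover 92–94%.

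Finally, the excess is only 0.9% to 6% of the restricted mean (0.15/17.55 to 0.92/15.14), and at 70–95% retention the median is simply not reached. Both are true. The excess is still large against the standard error, which is why coverage falls, and falls further as n rises from 50 to 100.

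**Conclusion.** The concern holds and the plan should be changed, though no planned test depends on it. That the visit-dated mean equals the upper limit of the 18-month restricted mean is exact, given visit dating and visits on schedule. The sizes of the bias, the shrinkage of a difference and the coverage rest on assumed retention and on how losses fall within intervals. At assumed 18-month retention of 70–80%, the dating rule, not scarcity of events, causes most of the loss of coverage. Confidence in the practical size is moderate, because neither the dating rule nor the expected retention is documented.

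**What to change.** - Make the reported summaries retention at 6, 12 and 18 months with 95% confidence intervals.
- Report the 18-month difference between materials and between isolation methods with an interval that respects the pairing within child: a paired difference in proportions, or a GEE clustered by child with material and isolation terms. Each child carries one of two material-by-isolation combinations (a with d, or b with c), so a contrast such as a against b is between children and cannot be paired.
- State whether the event is any loss or complete loss, and how a loss is dated.
- If a time-to-loss summary is kept, code each loss as falling after the previous visit and up to the current one, and use an interval-censored estimator or a discrete-time complementary log-log model clustered by child.
- At minimum, label the mean as visit-dated and restricted to 18 months, and print its lower limit, mean − 6 × (1 − S18), beside it.

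The cost is analysis-plan wording and a little extra analysis, with no new data. The drawback is a summary less familiar than mean survival in months.
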